## 7.0 STATISTICAL ANALYSIS

Unless otherwise specified, all statistical tests and confidence intervals (CIs) described in this document will be two-sided with alpha = .05. The SAS® statistical package (version 9.4 or a later version) will be used for the analyses.

The first dosing date is defined as the first date the subject received any study treatment. Subject disposition, demographics, and baseline characteristics will be summarized by treatment sequence and all subjects combined (Total). Adverse events (AEs) will be summarized by actual treatment received at the onset of the AE (Section 7.6.2). Efficacy analyses, laboratory tests, vital signs, ECG, and ECOG performance status will be summarized by treatment sequence and all subjects combined (Total), unless otherwise specified.

The following data listings by study center and subject ID will be provided: screened subjects (with reason for screen failure), disposition (with reasons for discontinuation of treatment and withdrawal from study), important protocol deviations, demographic and baseline characteristics, study drug administration, individual efficacy data, subjects excluded from the efficacy analysis, AEs, all deaths (including primary cause of death), serious adverse events (SAEs), other significant AEs (including treatment discontinuation due to AEs), concomitant medications, and the protocol specified laboratory measurements. Additional data listings may be generated to support other relevant discussions in Clinical Study Report.

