### 7.2 Demographic and Other Baseline Characteristics

The Randomized Subject Analysis Set (Section 5.2) will be used to summarize demographic and baseline characteristics. The demographic variables consist of age, age category (<18, 18-64, 65-84, ≥85 years), sex, ethnicity, and race. Baseline characteristics include height, weight, body

surface area (BSA), ECOG performance status, prior anticancer therapy if any including prior HMA treatment (decitabine or azacitidine), study disease (De Novo AML or Secondary AML), secondary AML specify (MDS, Other Antecedent Hematological Disorder, Therapy-related AML), FAB classification, time since diagnosis, cytogenetic risk classification, hemoglobin, neutrophils, platelets, bone marrow [BM] blast counts (%), peripheral blood [PB] blast counts), transfusion dependence (RBC and platelet). Race and ethnicity summaries will be based on the levels according to CDISC standards.

Baseline values are the last value collected before or on the 1st dosing date unless otherwise specified.

Time since diagnosis will be calculated as the (date of 1st dose – date of diagnosis). If the day is missing for date of diagnosis, the 15th of the month is used. If the month is missing, July 1st is used. If the year is missing, the date is left as missing. Complete details of imputation rules are presented in the Astex Data Programming Standards.

Subject demographic and baseline characteristics will be summarized by mean, standard deviation, median, minimum, and maximum for continuous variables; and by counts and percentages for categorical variables.

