## 7.6.2 Adverse Events

Adverse events reported by study subjects or observed by investigators will be mapped to the appropriate System Organ Class (SOC) and Preferred Term (PT) according to the Medical Dictionary for Regulatory Activities (MedDRA). Severity of AEs will be graded using Common Terminology Criteria for Adverse Events (CTCAE) version 4.03.

Treatment-emergent AEs (TEAEs) are defined as events that first occurred or worsened on or after the date of the first dose of study treatment until 30 days after the last dose of study treatment or until the start of a post-treatment alternative anti-leukemia treatment, whichever occurs first, with the following exceptions: events that occurred after 30 days beyond the last dose of study treatment or the start of a post-treatment alternative anti-leukemia treatment will also be considered treatment-emergent if the events are both serious and related to the study treatment. For the purpose of determining whether an AE is a treatment-emergent AE, incomplete AE start and stop dates will be imputed conservatively following the data programming conventions as detailed in the Astex Data Programming Standards.

All AE data collected in the study database with an AE start date on or before the data cutoff date will be included in the data listings, including those that are not treatment emergent. Only TEAEs will be included in the AE summary tables.

An overall safety summary table containing counts and percentages of subjects with any AE, any AE Grade  $\geq 3$ , AE leading to treatment discontinuation, any SAE, and subcategories of SAEs (death vs not death) will be produced.

Related events are those that the Investigator considered to be related to study treatment as described in the study protocol. All summaries of AEs will be made separately in the following groups:

- IV decitabine in Cycle 1 or Cycle 2.
- ASTX727 in Cycle 1 or Cycle 2.
- ASTX727 in Cycle 3 or later.
- Total for ASTX727.
- Total for the AML study.

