### **7.6.4 Laboratory Tests**

Laboratory values will also be graded, if possible, by CTCAE v4.03 in conjunction with the Harrison (18th edition) lab book normal values ([Longo et al 2011](#)). Shift tables will display (1) shift from baseline grade to the worst grade during the study, and (2) shift from baseline grade to the last grade at the end of study.

Laboratory values recorded as an interval such as " $\geq x$ ", " $< x$ ", or " $2+$ " will be handled, if necessary for calculation purposes, following the data programming standards as detailed in the ADaM data reviewer guide.

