#### **7.6.7      ECOG Performance Status**

Shift tables for ECOG from baseline to the worst grade, and from the baseline to the last available grade will be provided.

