**ASTX727-02 EMEA AML Submission****Population: Efficacy Analysis Set**

**Table xx.x.x**  
**Analysis of Overall Response**

	Sequence A (N=xx)		Sequence B (N=xx)		Total (N=xx)	
	n (%)	95% CI	n (%)	95% CI	n (%)	95% CI
Best Response						
CR	xx (xx.x)	(xx.x, xx.x)	xx (xx.x)	(xx.x, xx.x)	xx (xx.x)	(xx.x, xx.x)
CRi	xx (xx.x)	(xx.x, xx.x)	xx (xx.x)	(xx.x, xx.x)	xx (xx.x)	(xx.x, xx.x)
CRp	xx (xx.x)	(xx.x, xx.x)	xx (xx.x)	(xx.x, xx.x)	xx (xx.x)	(xx.x, xx.x)
PR	xx (xx.x)	(xx.x, xx.x)	xx (xx.x)	(xx.x, xx.x)	xx (xx.x)	(xx.x, xx.x)
SD	xx (xx.x)	(xx.x, xx.x)	xx (xx.x)	(xx.x, xx.x)	xx (xx.x)	(xx.x, xx.x)
PD	xx (xx.x)	(xx.x, xx.x)	xx (xx.x)	(xx.x, xx.x)	xx (xx.x)	(xx.x, xx.x)
NE	xx (xx.x)	(xx.x, xx.x)	xx (xx.x)	(xx.x, xx.x)	xx (xx.x)	(xx.x, xx.x)
Composite Response Rates						
CR + CRi	xx (xx.x)	(xx.x, xx.x)	xx (xx.x)	(xx.x, xx.x)	xx (xx.x)	(xx.x, xx.x)
CR + CRi + PR	xx (xx.x)	(xx.x, xx.x)	xx (xx.x)	(xx.x, xx.x)	xx (xx.x)	(xx.x, xx.x)
CR + CRp	xx (xx.x)	(xx.x, xx.x)	xx (xx.x)	(xx.x, xx.x)	xx (xx.x)	(xx.x, xx.x)
CR + CRh	xx (xx.x)	(xx.x, xx.x)	xx (xx.x)	(xx.x, xx.x)	xx (xx.x)	(xx.x, xx.x)
CRh 	xx (xx.x)	(xx.x, xx.x)	xx (xx.x)	(xx.x, xx.x)	xx (xx.x)	(xx.x, xx.x)

The 95% CI is Clopper-Pearson confidence interval.

CR=complete response; CRp=complete response with incomplete platelet recovery; CRi=CR with incomplete blood count recovery; PR=partial response; SD = Stable Disease; PD = Progressive Disease;

NE=Not evaluable. Subjects who did not have a valid post-treatment efficacy assessment (ie, no post-treatment BM/PB sample or the quality of BM/PB sample is not adequate for an assessment of efficacy) were classified as NE for response classifications.

(1) Modified 2003 IWG response criteria ([Cheson et al. 2003](#)) and DACO-016 CSR was used for CR, CRi, CRp, PR, SD, and PD, and NE.(2) [Kantarjian et al 2017](#) was used for the CRh assessment.

Sequence A: ASTX727 in Cycle 1; IV decitabine in Cycle 2. Sequence B: IV decitabine in Cycle 1; ASTX727 in Cycle 2.

Program Location: *m:\astx727\02\biostat\phase3\_eu\devel\program\tables\t\_response1.sas*, Data Cut Off: 04JUN2021, Database Extracted: 16JUL2021  
 Output: *t\_14.3.1\_response1.rtf* (Date Generated: 01SEP2021:13:56), Source Data: ADAMDATA.ADSL, ADRS

(2) ) using [2017 ELN](#) and [Kantarjian et al 2017](#)

<Protocol>

Population: <Analysis Set>

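### SAP 7.0, 7.6.4 and 7.6.7 tabulate laboratory and ECOG shifts by treatment sequence over the whole study, so graded laboratory data have no planned summary by drug

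*SAP*

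**What the plan says.** SAP 7.0 sets the default: "Efficacy analyses, laboratory tests, vital signs, ECG, and ECOG performance status will be summarized by treatment sequence and all subjects combined (Total", unless another section says differently.

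SAP 7.6.4 does not override this for laboratory tests. It plans two shift tables: "shift from baseline grade to the worst grade during the study" and "shift from baseline grade to the last grade at the end of study". SAP 7.6.7 does the same for performance status: "Shift tables for ECOG from baseline to the worst grade, and from the baseline to the last available grade will be provided". The general baseline rule in SAP 7.2 uses a single pre-treatment value: "Baseline values are the last value collected before or on the 1st dosing date unless otherwise specified". No Cycle 2 baseline is defined for laboratory tests or ECOG.

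The sequences are defined in the response table shell in SAP Appendix 1: "Sequence A: ASTX727 in Cycle 1; IV decitabine in Cycle 2. Sequence B: IV decitabine in Cycle 1; ASTX727 in Cycle 2". From Cycle 3 everyone takes ASTX727 (SAP 3.1).

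Elsewhere the SAP departs from the sequence default:

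- **Adverse events (7.6.2):** "All summaries of AEs will be made separately in the following groups". The groups are IV in either crossover cycle, ASTX727 in either crossover cycle, ASTX727 from Cycle 3, all ASTX727, and everyone.
- **Vital signs (7.6.5):** by visit and treatment group.
- **LINE-1 (7.4):** by treatment within each of Cycles 1 and 2, from that cycle's own baseline.

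**The concern.** In a crossover, sequence is the order of treatments and not a treatment. Worst grade is a maximum over cycles, so it largely ignores order. Two columns that differ only in order will look alike even if one drug causes clearly more grade 3 or 4 cytopenia than the other, and each column mixes an IV cycle into what should describe ASTX727.

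Long-term safety of ASTX727 is a secondary objective (SAP 2.2). The protocol's design discussion (4.2) argues that equivalent exposure predicts similar clinical performance. Myelosuppression is the toxicity that the protocol anticipates (7.6 and 8.3). A by-drug view of graded blood counts is the natural descriptive support for that argument, and randomization makes Cycle 1 a between-drug comparison free of carryover. If the by-drug tables are not planned, producing them later would be post hoc.

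**Working it through.** The documents give no laboratory toxicity rates, and no stated figure bears on this point, so there is nothing of the plan's own to reproduce. The rates below are assumptions chosen to show the structure.

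**Inputs**

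- pA, pI: per-cycle probability of a severe laboratory grade on ASTX727 and on IV. Assumed 0.40 and 0.20, then reversed.
- K: number of cycles received. Two, to isolate the crossover, and six, because the table covers the whole study.
- d: share stopping after Cycle 1, the same in both sequences. Assumed 0, 0.10 and 0.20. The last borrows, as an assumed ceiling, the non-evaluable share of about 20% in SAP 4.0.
- Cycles independent, no carryover.

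**Step 1. Subjects who receive both drugs.** Either order gives one IV cycle and K − 1 ASTX727 cycles:

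P(worst grade severe) = 1 − (1 − pI)(1 − pA)^(K−1)

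Order does not appear, so the two sequences have the same value for any pair of rates.

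| pA, pI | K | Sequence A | Sequence B |
|---|---|---|---|
| 0.40, 0.20 | 2 | 1 − 0.8×0.6 = 0.520 | 0.520 |
| 0.20, 0.40 | 2 | 1 − 0.6×0.8 = 0.520 | 0.520 |
| 0.40, 0.20 | 6 | 1 − 0.8×0.6^5 = 0.938 | 0.938 |
| 0.20, 0.40 | 6 | 1 − 0.6×0.8^5 = 0.803 | 0.803 |

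**Step 2. Early stoppers.** A subject who stops after Cycle 1 has had ASTX727 only in Sequence A and IV only in Sequence B. The difference between sequences becomes

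d×pA + (1 − d)×P − [d×pI + (1 − d)×P] = d×(pA − pI)

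With 0.40 and 0.20 this is 0.10×0.20 = 0.02 at d = 0.10, and 0.20×0.20 = 0.04 at d = 0.20. At K = 6 and d = 0.20 the columns are 0.830 and 0.790. The true per-cycle difference is 0.20.

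**Step 3. Does any column isolate ASTX727?** Five ASTX727 cycles alone give 1 − 0.6^5 = 0.922 at pA = 0.40, against 0.938 with the IV cycle included. At pA = 0.20 and pI = 0.40 the figures are 1 − 0.8^5 = 0.672 against 0.803. The columns respond to ASTX727's risk, but each, including Total, also contains the IV cycle.

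**Step 4. By-drug grouping.** A Cycle 1 table by drug received compares 0.40 with 0.20 directly. Under the same assumptions, so do the two crossover-cycle columns of SAP 7.6.2.

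**Step 5. Are the data there?** In the supplied protocol (Table 9 notes), hematology is weekly through Cycle 2, so per-cycle worst grades can be derived. Chemistry is scheduled at Screening, pre-dose on Day 1 from Cycle 2, and at discontinuation. ECOG follows the same pattern, plus the 30-day follow-up. For subjects who continue, the first scheduled post-dose chemistry or ECOG value is thus pre-dose on Cycle 2 Day 1. It can be used by drug only if a rule assigns it to the Cycle 1 drug.

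**The case against.** The strongest reply is that the information is not lost:

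- Clinically significant laboratory abnormalities count as AEs (protocol 10.1.1). SAP 7.6.2 tabulates AEs by drug and period, with summaries by CTCAE grade, so cytopenias reported as AEs already have IV and ASTX727 columns.
- Protocol-specified laboratory measurements are listed by subject (SAP 7.0).
- The last-grade table reflects ASTX727 for anyone reaching Cycle 3.
- The safety objective concerns ASTX727 itself, not a contrast with IV, and no primary endpoint or decision rule is affected.

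Most of this stands, and it limits the point. It does not remove it. AE reporting depends on the investigator's judgement of significance, and protocol 10.2 asks for signs and laboratory results to be grouped under one diagnosis. Systematic grading of every value is what shift tables add. A listing is not a summary. The last-grade table is also by sequence, misses the nadir and offers no IV comparison.

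A reader might infer three stronger things that the documents do not support:

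- **That the tables show nothing about ASTX727's laboratory toxicity.** Over six cycles the assumed rates give 94%, and 80% when reversed, so the columns do move with ASTX727's risk. The 52% that stays the same on reversal is particular to a two-cycle horizon, whereas the planned table covers the whole study.
- **That the sequences match from Cycle 2 on.** In Cycle 2 itself they receive opposite drugs. Only the cumulative content matches, once Cycle 2 is complete.
- **That the MDS/CMML shift tables share the fault.** Protocol 11.8 states no grouping for them, and SAP 1.0 says that they fall under a separate SAP, which was not supplied.

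**Conclusion.** The point holds as a limited gap. For subjects who receive both drugs, the planned sequence columns carry about no drug contrast in worst grade, and early stopping restores only d×(pA − pI): 2 to 4 percentage points for a true 20 when 10% to 20% stop after Cycle 1. No worst-grade column separates ASTX727 from IV decitabine. What is missing is a planned by-drug summary of systematically graded laboratory values. By-drug reporting of laboratory AEs and the listings remain in place.

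The exact cancellation assumes independent cycles and no carryover, and the residue assumes equal stopping in both sequences. The rates are illustrative, but the cancellation does not depend on them. The sampling schedule comes from the supplied US MDS/CMML protocol and is assumed to apply to the AML subjects whom this SAP covers. The case is strongest for hematology. The primary PK analysis is untouched, so this is a cheap improvement and not a flaw in the trial's main conclusion.

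**What to change.** - In SAP 7.6.4, produce the worst-grade shift tables in the columns of 7.6.2: IV in Cycle 1 or 2, ASTX727 in Cycle 1 or 2, ASTX727 in Cycle 3 or later, total ASTX727, and total. Amend the default in 7.0 to match.
- For hematology, add a worst-grade table for Cycle 1 only, by drug received.
- For hematology in Cycle 2, use the pre-dose Cycle 2 Day 1 grade as an additional baseline beside the study baseline.
- State that a pre-dose Day 1 value is attributed to the drug of the preceding cycle. With that rule, the same columns can be used for chemistry and for ECOG in 7.6.7.

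The cost is SAP wording and a few more tables, with no new data if the AML schedule matches the supplied one. The downside is more columns, and Cycle 2 values carry some Cycle 1 effect. The Cycle 1 hematology table avoids that effect. No change is requested to the MDS/CMML tables.

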### 7.1 Subject Disposition

Subject disposition including number of subjects randomized (enrolled), treated, and treatment discontinuation by reason, as well as reasons for withdrawal from study (ie, death, complete consent withdrawal, or lost to follow-up) and subjects ongoing at data-cut will be summarized using frequencies and percentages based on information collected on the study case report form pages. Subjects in the Randomized Subject Analysis Set will be included in the disposition analysis. A separate screening summary, based on the All Subjects Analysis Set, will include the number of subjects who were screened, failed screening and the reasons for screen failure.

### 7.2 Demographic and Other Baseline Characteristics

The Randomized Subject Analysis Set (Section 5.2) will be used to summarize demographic and baseline characteristics. The demographic variables consist of age, age category (<18, 18-64, 65-84, ≥85 years), sex, ethnicity, and race. Baseline characteristics include height, weight, body

surface area (BSA), ECOG performance status, prior anticancer therapy if any including prior HMA treatment (decitabine or azacitidine), study disease (De Novo AML or Secondary AML), secondary AML specify (MDS, Other Antecedent Hematological Disorder, Therapy-related AML), FAB classification, time since diagnosis, cytogenetic risk classification, hemoglobin, neutrophils, platelets, bone marrow [BM] blast counts (%), peripheral blood [PB] blast counts), transfusion dependence (RBC and platelet). Race and ethnicity summaries will be based on the levels according to CDISC standards.

Baseline values are the last value collected before or on the 1st dosing date unless otherwise specified.

Time since diagnosis will be calculated as the (date of 1st dose – date of diagnosis). If the day is missing for date of diagnosis, the 15th of the month is used. If the month is missing, July 1st is used. If the year is missing, the date is left as missing. Complete details of imputation rules are presented in the Astex Data Programming Standards.

Subject demographic and baseline characteristics will be summarized by mean, standard deviation, median, minimum, and maximum for continuous variables; and by counts and percentages for categorical variables.

### **7.3 Pharmacokinetics Analyses**

The primary endpoint analysis includes data from the following PK assessment days to calculate the 5-day total cycle AUC:

- ASTX727 AUC0-24: Days 1, 2, and/or 5.
- IV decitabine AUC0-24: Days 1 and/or 5.

All details regarding the analyses of the primary and secondary PK endpoints are provided in a separate PAP.

### **7.4 Pharmacodynamic (LINE-1) Analyses**

The PD (LINE-1) Analysis Set (Section 5.6) will be used for analyses of LINE-1 methylation. Since LINE-1 methylation levels often do not completely return to baseline by Day 28 of Cycle 1, and to avoid the confounding effects of differing baselines in Cycle 2 vs Cycle 1, subjects will be compared for each of the 2 cycles separately using the baseline values prior to each cycle, thus limiting the evaluation to interpatient comparisons in each of the 2 cycles.

For each of Cycles 1 and 2, LINE-1 methylation data will be summarized descriptively (using mean, standard deviation, standard error, median, minimum and maximum) by visit and treatment. Descriptive statistics for maximum %LINE-1 demethylation will be summarized by treatment.

In addition, the 95% CIs for mean maximum %LINE-1 demethylation in Cycles 1 and 2 will be provided for ASTX727 and IV decitabine, respectively. The 95% CI for the difference in mean

maximum %LINE-1 demethylation between ASTX727 and IV decitabine in Cycles 1 and 2 will also be generated based on an analysis of variance (ANOVA) model with treatment as factor.

## 7.5 Efficacy Variables and Analyses

Efficacy analyses will be based on the Efficacy Analysis Set (Section 5.3). Efficacy variables will be summarized using descriptive statistics and there will be no formal comparison analyses between treatment sequences.

### 7.5.1 Response Rate

The evaluation of response (Table 2) will be based on Modified IWG 2003 AML Response Criteria (Cheson et al 2003), and include CRp according to the DACO-016 study (Kantarjian et al 2012) for that CRp is not any response category of IWG 2003 AML Response Criteria (Cheson et al 2003). Subjects who do not have a valid post-treatment efficacy assessment (ie, no post-treatment BM/PB sample or the quality of BM/PB sample is not adequate for an assessment of efficacy) will be classified as not evaluable (NE) for response classifications. Subjects who cannot be classified into a response category (CR, CRi, or PR) or into the NE category will be classified as non-responders (NR). According to the recommendations of the European LeukemiaNet (Döhner et al 2017), progressive disease is defined as >50% increase in marrow blast % from baseline (15% increase in cases with <30% marrow blasts at baseline); or >70% marrow blasts over at least 3 months; or >50% increase in peripheral blasts to  $\geq 25 \times 10^9/L$  ( $\geq 25,000/\mu L$ ); and stable disease is defined as absence of CR, CR subtype, PR and progressive disease for at least 3 months. CRh, CR with partial hematologic recovery, is defined as <5% of blasts in the bone marrow, no evidence of disease, and partial recovery of peripheral blood counts (platelets  $>50,000/\mu L$  and ANC  $>500/\mu L$ ) (Kantarjian et al 2017). Evaluation of response will be conducted by Astex medical monitors assisted by programmed data listings, as detailed in the Astex AML Response Assessment Criteria (Section 8.1).

**Table 2: Modified IWG 2003 AML Response Criteria**

Response a	ASTX727-02 Specific Criteria
CR	ANC $\geq$ 1000/ $\mu$ L, Platelets $\geq$ 100,000/ $\mu$ L, independence from RBC and platelet transfusions over the past week, no leukemic blasts b <5% leukemic blasts
CRi	All CR criteria except ANC <1000/ $\mu$ L or Platelets <100,000/ $\mu$ L
CRp	All CR criteria except Platelets <100,000/ $\mu$ L and platelet transfusions over the past week
PR	All CR criteria except decrease of $\geq$ 50% in leukemic blasts to level of 5% to 25%

ANC=absolute neutrophil count; CR=complete response; CRp=complete response with incomplete platelet recovery; CRi=CR with incomplete blood count recovery; PR=partial response.

a Responses are based on both PB and BM conditions.

b For the purpose of response assessment and according to published IWG criteria, blasts may be seen in PB as rare PB blasts may be identified during regeneration, but the subject is in CR if BM blasts are <5% with no Auer rods.

Source: [Cheson et al 2003](#); [Kantarjian et al 2012](#)

For subjects who experience different response levels at different visits, the best response (see [Table 2](#)) will be used for summary and analyses. Overall objective response will be the number of subjects achieving CR, CRi, and PR with each subject counted once according to their best response. CRp, a subcategory of CRi will be listed under CRi. Composite response rates, CR + CRi (either CR or CRi), CR + CRi + PR (either CR or CRi or PR), CR + CRh (either CR or CRh) and CRh, will also be included in the response analysis.

Subjects with these different response categories will be listed and summarized using frequency counts and proportion of subjects with each category. The 95% Clopper-Pearson confidence interval will be provided for each response rate. Subgroup analyses such as by age category ( $<75$ ,  $\geq 75$ ) may be performed.

